2.4.1.3 Cumulative dose

Cumulative dose of a study treatment is defined as the total dose given during the study treatment exposure and will be summarized for each of the study treatment components, respectively.

The **planned cumulative dose** for a study treatment component refers to the total planned dose as per the protocol up to the last date of investigational drug administration. The planned cumulative dose is not summarized/listed. It is used for relative dose intensity calculations.

The **actual cumulative dose** refers to the total actual dose administered, over the duration for which the subject is on the study treatment as documented in the study treatment eCRF.

For subjects who did not take any drug, the actual cumulative dose is by definition equal to zero for that drug.

For capmatinib (continuous dosing), the actual cumulative dose is the sum of the non-zero doses recorded over the dosing period. The planned cumulative dose is the planned starting dose summed over the same dosing period.

For pembro (intermittent dosing), the actual cumulative dose should be defined based on the days when the subject is assumed to have taken a non-zero dose during dosing periods (number of infusions taken over the treatment period). The planned cumulative dose is the planned starting dose summed over the number of expected infusions during treatment period (e.g, a subject treated for 63 days is expected to have three infusions).

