6.1.3 Treatment arms

Subjects will be assigned to one of the following two treatment arms in a ratio of 2:1. A complete cycle of treatment is defined as 21 days of an infusion of pembrolizumab, with or without continuous capmatinib treatment.

- Capmatinib 400 mg (tablets) orally twice daily (BID) followed by pembrolizumab 200 mg intravenously (i.v.) on day 1 of each cycle, every 21 days.
- Pembrolizumab 200 mg intravenously (i.v.) alone every 21 days.

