- On days that blood PK samples are obtained, the subject should take the dose in the clinic after pre-dose PK samples and prior to post-dose PK samples (if applicable), when instructed by the study staff. The exact time of drug administration should be recorded in the appropriate eCRF. If a subject vomits within 4 hours of capmatinib dosing, the time of vomiting should be recorded on the eCRF. If vomiting occurs during the course of treatment, then no re-dosing of capmatinib is allowed before the next scheduled dose.
- During the whole duration of treatment with capmatinib, the subject is recommended to use precautionary measures against ultraviolet exposure (e.g., use of sunscreen, protective clothing, avoid sunbathing or using a solarium).

The orally administered film-coated tablet formulation will be provided in two strengths of 150 mg and 200 mg free base equivalent. For the list of excipients, please refer to the current capmatinib Investigator's Brochure.

Pembrolizumab

Pembrolizumab (100 mg concentrate for solution for infusion or 50 mg lyophilized powder for reconstitution for infusion) will be administered intravenously at 200 mg once every 21 days. Further instructions for the preparation, administration and infusion durations of pembrolizumab should follow the locally approved package insert.

Study treatment schedule adjustment

After the first dose, there will be a ± 4 -day window for the administration of pembrolizumab in the subsequent cycles. If a dose cannot be administered within the planned window due to any unresolved AEs, the dose on that cycle should be skipped. The subsequent dose should be administered in the next scheduled cycle or when the AE has been resolved/recovered for dose continuation as specified in [Section 6.5.1](#).

In the combination therapy, if one of the study drugs is permanently discontinued due to any unresolved AEs, the other study drug can be continued. For more details of treatment duration, please refer to [Section 6.1.4](#).

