2.4.1.4 Dose intensity and relative dose intensity

For dose intensity calculations, the unit of time for capmatinib will be days and for pembro will be cycles.

For capmatinib, the **dose intensity** (DI) is defined as follows:

$DI \text{ (mg/day)} = \text{actual cumulative dose (mg)} / \text{duration of exposure to capmatinib (days)}$.

For example:

The duration of exposure is 56 days and the subject received 50 days of full dosing

$DI \text{ (mg/day)} = 40,000 \text{ (mg)} / 56 \text{ (days)} = 714 \text{ (mg/day)}$

For pembro, the **dose intensity** (DI) is defined as follows:

$DI \text{ (mg/cycle)} = \text{length of cycle} \times (\text{actual cumulative dose (mg)} / \text{duration of exposure to pembro (days)})$.

For example:

The duration of exposure is 63 days and the subject received three complete infusions

$DI \text{ (mg/cycle)} = 21 \text{ (days)} \times (600 \text{ (mg)} / 63 \text{ (days)}) = 200 \text{ (mg/cycle)}$

For subjects who did not take any drug, the DI is by definition equal to zero.

For capmatinib, the **planned dose intensity** (PDI) is defined as follows:

$\text{PDI (mg/day)} = \text{planned cumulative dose (mg)} / \text{duration of exposure to capmatinib (days)}$

For example:

The duration of exposure is 56 days and the subject is planned to receive 56 days of dosing

$\text{PDI (mg/day)} = 44,800 \text{ (mg)} / 56 \text{ (days)} = 800 \text{ (mg/day)}$

For pembro, the **planned dose intensity** (PDI) is defined as follows:

$\text{PDI (mg/cycle)} = \text{length of cycle} \times (\text{planned cumulative dose (mg)} / \text{duration of exposure to pembro (days)})$.

For example:

The duration of exposure is 63 days and the subject is planned to receive three infusions

$\text{PDI (mg/cycle)} = 21 \text{ (days)} \times (600 \text{ (mg)} / 63 \text{ (days)}) = 200 \text{ (mg/cycle)}$

Relative dose intensity (RDI) is defined as follows:

$\text{RDI} = \text{DI (mg/unit of time)} / \text{PDI (mg/unit of time)}$

DI and RDI will be summarized separately for each of the study treatment components, using the duration of exposure of each of the components. RDI will be summarized in percentages. Summary of RDI will include categorical summaries. The RDI categories are $< 50\%$, $\geq 50\% - < 75\%$, $\geq 75\% - < 90\%$, $\geq 90\% - < 110\%$ and $\geq 110\%$.

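### Pembrolizumab relative dose intensity reduces to infusions given over infusions expected, and the SAP does not say how to count the expected ones unless exposure is a multiple of 21 days

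*SAP*

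**What the plan says.** The protocol plans the same pembrolizumab dose in both arms; section 6.1.3 gives the control arm as "Pembrolizumab 200 mg intravenously (i.v.) alone every 21 days". Section 6.7.2 allows, after the first dose, a plus or minus "4 -day window for the administration of pembrolizumab in the subsequent cycles". If an unresolved adverse event pushes a dose outside that window, "the dose on that cycle should be skipped", and then: "The subsequent dose should be administered in the next scheduled cycle or when the AE has been resolved/recovered for dose continuation".

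SAP 2.4.1.3 first defines planned cumulative dose for any component as the "total planned dose as per the protocol up to the last date of investigational drug administration". For pembrolizumab it then says: "The planned cumulative dose is the planned starting dose summed over the number of expected infusions during treatment period". The one illustration is that "a subject treated for 63 days is expected to have three infusions".

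SAP 2.4.1.4 sets dose intensity (DI) at 21 × actual cumulative dose / duration, planned dose intensity (PDI) at 21 × planned cumulative dose / duration, and RDI = DI/PDI. Its PDI example is the same case: "The duration of exposure is 63 days and the subject is planned to receive three infusions". RDI is tabulated in five bands: below 50%, 50 to below 75%, 75 to below 90%, 90 to below 110%, and 110% or more.

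SAP 2.4.1.1 takes the last pembrolizumab exposure date as the last dose date plus 20 days. It then computes duration as that date minus the first dose date, plus a further 20.

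**The concern.** PDI should state what the protocol planned per unit of time, so that RDI falls smoothly as doses are delayed. Capmatinib behaves this way: its planned dose is summed over the same days that form the denominator, and PDI in the SAP example is 44,800/56 = 800 mg/day. For pembrolizumab the planned dose is a number of infusions and the time element cancels. RDI then depends on how that number is obtained, and the SAP shows this only for a duration where every method agrees.

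Other durations will be routine, given the dosing window, restart once an adverse event has resolved, and truncation of exposure at death, loss to follow-up or data cut-off (SAP 2.4.1.1). Two programmers could produce different RDI tables from the same data. Enrolment was halted for tolerability in the combination arm, so readers will look at the exposure tables.

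**Working it through.** **Inputs.** Planned dose 200 mg per 21 days (Protocol 6.1.3); window ±4 days (Protocol 6.7.2); formulas and bands from SAP 2.4.1.3 and 2.4.1.4. Duration is taken as (last dose + 20) − first dose + 1, because that is what gives 63 days for infusions on Days 1, 22 and 43.

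**The SAP's own figure.** DI = 21 × 600/63 = 200 mg/cycle; PDI = 21 × 600/63 = 200 mg/cycle; RDI = 100%. Reproduced.

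**Cancellation.** RDI = [21 × 200 × given / duration] / [21 × 200 × expected / duration] = given / expected.

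**Two ways to count, both grounded in SAP 2.4.1.3.** Scheduled infusions fall on Days 1, 22, 43, 64 and so on. They can be counted over the exposure period (to last dose + 20) or up to the last administration date. The pro-rated value is 21 × given / duration.

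| Infusion days | Duration | Over exposure period | Up to last administration | Pro-rated |
|---|---|---|---|---|
| 1, 22, 43 | 63 | 3/3 = 100% | 3/3 = 100% | 63/63 = 100% |
| 1, 22, 44 | 64 | 3/4 = 75% | 3/3 = 100% | 63/64 = 98.4% |
| 1, 22, 42 | 62 | 3/3 = 100% | 3/2 = 150% | 63/62 = 101.6% |
| 1, 22, 47 | 67 | 3/4 = 75% | 3/3 = 100% | 63/67 = 94.0% |
| 1, 22, 39 | 59 | 3/3 = 100% | 3/2 = 150% | 63/59 = 106.8% |
| 1, 22, 57 | 77 | 3/4 = 75% | 3/3 = 100% | 63/77 = 81.8% |
| 1, 22, 64 | 84 | 3/4 = 75% | 3/4 = 75% | 63/84 = 75.0% |

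Rows two to five are shifts within the window. Their pro-rated values all lie in the 90 to below 110% band, while the counts can give 75% or 150%, each in a different band. In the Day 57 row, a 14-day delay reads as 100% under one count. A whole skipped cycle (last row) is captured correctly by both.

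**Dependence on the number of infusions.** The late-shift value is n/(n+1) and the early-shift value n/(n−1).

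| n | n/(n+1) | n/(n−1) |
|---|---|---|
| 2 | 66.7% | 200% |
| 3 | 75.0% | 150% |
| 6 | 85.7% | 120% |
| 9 | 90.0% | 112.5% |
| 18 | 94.7% | 105.9% |
| 35 | 97.2% | 102.9% |

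A late shift no longer leaves the 90 to below 110% band from 9 infusions (9/10 = 90%). An early shift no longer does from 12 (12/11 = 109.1%).

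**Duration as written.** For Days 1, 22 and 43 the last exposure date is Day 63, and 63 − 1 + 20 = 82 days, against 63 in the SAP's example. With that duration DI = 21 × 600/82 = 153.7 mg/cycle, and DI/200 = 76.8% for perfect dosing.

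**The case against.** The strongest reply is that the SAP states no whole-number or rounding rule. A reader might infer one from a count of infusions, but the 63-day example fits duration/21 unrounded equally well, and on that reading RDI is already pro-rated. Rounding to the nearest whole number would also give 100% for three infusions with the last one shifted by up to 4 days. The SAP Introduction places derived-variable specifications in a separate programming document, which may settle the rule. This stands: the defect is an unspecified count whose natural readings misbehave, not a stated wrong rule.

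A reader might also infer that one dosing pattern yields 75%, 100% and 150%. It does not: 75% needs a late dose and one way of counting, and 150% an early dose and the other.

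Nor do the documents support saying that delays are concealed. DI in mg/cycle is summarised alongside RDI (SAP 2.4.1.4), interruptions and their reasons are tabulated (2.4.2), all doses are listed (2.4.4), and adverse events leading to interruption or discontinuation are reported (2.8.1). Those events, not RDI, are the listed safety endpoint. It is tempting to add that the error is larger in the combination arm, or to quote a share of subjects misclassified. Either would need a rate of dose slippage by arm, which the documents do not give.

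What remains is that RDI is a prespecified by-arm summary with no reproducible derivation for ordinary dosing patterns.

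**Conclusion.** The point holds as a gap in the derivation. When expected infusions are read as a count of scheduled doses, a one-day shift within the window changes RDI by one whole infusion: 75% against a pro-rated 98%, or 150% against 102%, for three infusions. The effect is confined mainly to subjects with few infusions and shrinks to about 97% to 103% at 35. These figures assume the duration convention implied by the 63-day example. The double addition of 20 days in SAP 2.4.1.1 is a separate written contradiction of that example and has to be resolved with it. RDI is descriptive, so neither the primary analysis nor the adverse-event tables change.

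**What to change.** Make these edits together:

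1. SAP 2.4.1.4: define pembrolizumab PDI as the protocol's planned 200 mg per 21-day cycle, so that RDI = DI/200. Equivalently, expected infusions = duration/21, unrounded. This concerns the analysis denominator only.
2. SAP 2.4.1.1: make the duration formula agree with the worked examples, as (last dose + 20) − first dose + 1. Edit 1 made without this would give 76.8% for three on-time infusions.
3. SAP 2.4.1.3: make the general wording that ends planned dose at the last administration consistent with the exposure period used for pembrolizumab. The two coincide for capmatinib but differ by 20 days for pembrolizumab.
4. State how truncated exposure enters RDI. As an illustration, one infusion followed by death on Day 6 gives a duration of 6 days, DI = 21 × 200/6 = 700 mg/cycle and a pro-rated RDI of 350%. DI as already planned has the same feature.

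The cost is a few SAP lines and one derivation. No new data are needed.

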2.4.1.4 Dose intensity and relative dose intensity

For dose intensity calculations, the unit of time for capmatinib will be days and for pembro will be cycles.

For capmatinib, the **dose intensity** (DI) is defined as follows:

$DI \text{ (mg/day)} = \text{actual cumulative dose (mg)} / \text{duration of exposure to capmatinib (days)}$.

For example:

The duration of exposure is 56 days and the subject received 50 days of full dosing

$DI \text{ (mg/day)} = 40,000 \text{ (mg)} / 56 \text{ (days)} = 714 \text{ (mg/day)}$

For pembro, the **dose intensity** (DI) is defined as follows:

$DI \text{ (mg/cycle)} = \text{length of cycle} \times (\text{actual cumulative dose (mg)} / \text{duration of exposure to pembro (days)})$.

For example:

The duration of exposure is 63 days and the subject received three complete infusions

$DI \text{ (mg/cycle)} = 21 \text{ (days)} \times (600 \text{ (mg)} / 63 \text{ (days)}) = 200 \text{ (mg/cycle)}$

For subjects who did not take any drug, the DI is by definition equal to zero.

For capmatinib, the **planned dose intensity** (PDI) is defined as follows:

$\text{PDI (mg/day)} = \text{planned cumulative dose (mg)} / \text{duration of exposure to capmatinib (days)}$

For example:

The duration of exposure is 56 days and the subject is planned to receive 56 days of dosing

$\text{PDI (mg/day)} = 44,800 \text{ (mg)} / 56 \text{ (days)} = 800 \text{ (mg/day)}$

For pembro, the **planned dose intensity** (PDI) is defined as follows:

$\text{PDI (mg/cycle)} = \text{length of cycle} \times (\text{planned cumulative dose (mg)} / \text{duration of exposure to pembro (days)})$.

For example:

The duration of exposure is 63 days and the subject is planned to receive three infusions

$\text{PDI (mg/cycle)} = 21 \text{ (days)} \times (600 \text{ (mg)} / 63 \text{ (days)}) = 200 \text{ (mg/cycle)}$

Relative dose intensity (RDI) is defined as follows:

$\text{RDI} = \text{DI (mg/unit of time)} / \text{PDI (mg/unit of time)}$

DI and RDI will be summarized separately for each of the study treatment components, using the duration of exposure of each of the components. RDI will be summarized in percentages. Summary of RDI will include categorical summaries. The RDI categories are $< 50\%$, $\geq 50\% - < 75\%$, $\geq 75\% - < 90\%$, $\geq 90\% - < 110\%$ and $\geq 110\%$.

2.4.2 Dose reductions, interruptions and permanent discontinuations

The number of subjects who have dose reductions, permanent discontinuations or interruptions, and the reasons, will be summarized separately for each of the study treatment components.

The 'Type of change' field from the study treatment CRF pages will be used to determine the dose interruptions. Dose reductions will be derived programmatically using the dosing information as described below.

The corresponding fields 'Reason for change' will be used to summarize the reasons.

A dose change is recorded when 'Dose change' is entered on the 'Type of change' field on the DAR CRF page, where actual dose administered/total daily dose is different from the prescribed dose.

A dose interruption is recorded when 'Dose interruption' is entered on the 'Type of change' field on the DAR CRF page, where dose administered is interrupted.

For the purpose of summarizing interruptions and reasons, cases where multiple entries for interruption are entered on consecutive days with different reasons will be counted as separate interruptions. However, if the reason is the same in the mentioned multiple entries on consecutive days, then it will be counted as one interruption.

Dose reduction (only for capmatinib): A dose change where the prescribed dose level is lower than the previous prescribed dose level or where the actual dose administered/total daily dose is lower than the calculated dose amount based on the prescribed dose. Therefore any dose change to correct a dosing error will not be considered a dose reduction. Only the dose change

is collected in the CRF; the number of reductions will be derived programmatically based on the change and the direction of the change.

Dose interruption: Actual dose administered is equal to zero, between the first and last non-zero doses, following a non-zero actual dose administered. Number of dose interruptions and corresponding reason will be summarized.

2.4.3 Concomitant and post therapies

Summaries and listings described in this section will be based on the FAS.

2.4.3.1 Prior anti-neoplastic therapy

All prior anti-neoplastic medication, radiotherapy and surgery will be listed.

The number (%) of subjects who received any prior anti-neoplastic medication, radiotherapy or surgery will be summarized.

The summary of prior anti-neoplastic medications will include the total number of regimens (note: there can be more than one medication per regimen), therapy type at last treatment, setting at last treatment. Prior anti-neoplastic medications will also be summarized by ATC class, and PT.

The summary of prior anti-neoplastic radiotherapy will include the radiotherapy locations, (including all locations recorded for each subject), setting at last radiotherapy, and best response at last radiotherapy.

The summary of prior anti-neoplastic surgery will include the time (in months) between the last surgery to start of study treatment, procedure at last surgery and residual disease at last surgery.

Imputation rules for partially missing dates are provided in [Section 5.1.3.1](#).

2.4.3.2 Post treatment anti-neoplastic therapy

Anti-neoplastic therapies (medications, radiotherapies and surgeries) since discontinuation of study treatment will be listed.

2.4.3.3 Concomitant therapies

Concomitant therapies are defined as all interventions (therapeutic treatments and procedures) other than the study treatment administered to a subject coinciding with the study treatment period. Concomitant therapy include medications (other than study drugs) starting on or after the start date of study treatment or medications starting prior to the start date of study treatment and continuing after the start date of study treatment. Concomitant medications will be listed by subject and summarized by ATC class and treatment arm.

The summaries will include:

- Medications starting on or after the start of study treatment but no later than 30 days after last dose of study treatment and
- Medications starting prior to start of study treatment and continuing after the start of study treatment.

The imputation of a concomitant medication start date will follow the same conventions as for an AE start date. No imputation will be performed for concomitant medication end dates.

2.4.4 Compliance

Compliance to the study drug is presented by the number of dose reductions and dose interruptions, and the reasons. Subject level listings of all doses administered on-treatment along with dose change reasons will be produced.

2.5 Analysis of the primary objective

The primary endpoint of this study is the PFS. Estimation of PFS will be provided by treatment arm, and will be analyzed based on the FAS population.

2.5.1 Definition of primary endpoint

PFS is defined as the time from the date of randomization to the date of the first documented progression or death due to any cause. PFS will be assessed via local review according to RECIST 1.1.

2.5.2 Statistical hypothesis, model, and method of analysis

Due to the study enrolment halt on 21-Jan-2021, the discontinuation of capmatinib in the combination arm and the stopping of efficacy data collection in the eCRF, the initially planned Bayesian PFS analyses for the primary endpoint will become uninterpretable and this study is no longer expected to meet its primary endpoint. As mentioned in Section 12.8 of the current protocol, the Bayesian model will not be performed and the primary endpoint will be summarized instead using KM curves for PFS for each treatment arm. The FAS will be used. Median PFS, with corresponding 95% CI, and 25th and 75th percentiles ([Brookmeyer and Crowley 1982](#), [Klein and Moeschberger 1997](#)) will be presented. KM estimates for PFS proportions at specific timepoints (3, 6, 12, and 18 months), along with 95% CI (Greenwood's formula, [Kalbfleisch and Prentice 2002](#)) will also be provided. The number (%) of events and subjects censored will also be summarized.

2.5.3 Handling of missing values/censoring/discontinuations

PFS will be censored at the date of the last adequate tumor assessment prior to the earliest cut-off date for the analysis, the start of a subsequent anti-neoplastic therapy (if any), the date of sponsor's decision to discontinue capmatinib (applicable only to subjects on the combination arm), or if the event occurred after two or more missing tumor assessments. Clinical progression without objective radiological evidence will not be considered as documented disease progression. Subjects should be followed after discontinuation of treatment to document clinical progression. The date of the last adequate tumor assessment is the date of the last tumor assessment with overall lesion response of CR, PR or SD before an event or a censoring reason has occurred. If no post-baseline assessments are available (before an event or a censoring reason occurred), the date of treatment randomization will be used.

The number of subjects censored and reasons for censoring will be summarized by treatment arm using descriptive statistics.

2.5.4 Supportive analyses

To further explore the potential lasting effect of capmatinib, a supportive analysis of PFS will be performed without censoring data before the date of sponsor's decision to discontinue capmatinib. KM curves for such PFS as well as estimated median PFS along with their two-sided 95% CIs will be presented for each treatment arm.

